3.3.1.1 Dose Modification for Sunitinib related hypertension

Increases in blood pressure (BP) and cases of hypertension have been associated with many drugs acting on the VEGF pathway. The proposed mechanism for this increase is through inhibition of VEGF-induced peripheral vasodilation. Hypertension following sunitinib treatment has rarely been seen in animal studies or clinical trials. Dose modification guidelines are provided below and will be used in this protocol. Please see Section 4.1.1 for medical management guidelines.

Table 6 Recommended Dose Modification Hypertension Monitoring and Management

Grade (CTCAE v4)	Antihypertensive Therapy	Blood Pressure Monitoring	Sunitinib Dose Modification
Persistent Grade 1 Pre-hypertension Systolic 120-139 Diastolic 80-90		Standard	No change
Persistent Grade 2-Moderate Systolic 140-159 Diastolic 90-99 Protocol-specific guidance supersedes any other management guidelines, including	Step 1) Initiate LA DHP CCB treatment and if needed, after 24-48 hr. Rx, increase dose in stepwise fashion every 24-48 hours until BP is controlled or at max dose of Rx Step 2) If BP still not controlled, add another	BP should be monitored as recommended by the treating physician	No change except as described in step 4

Grade (CTCAE v4)	Antihypertensive Therapy	Blood Pressure Monitoring	Sunitinib Dose Modification
CTCAE v4	
antihypertensive Rx, a BB, ACE1, ARB, or ABB; increase dose of this drug as described in step 1
 
Step 3) If BP still not controlled, add 3rd drug from the list of antihypertensives in step 2; increase dose of this drug as described in step 1
 
Step 4) If BP still not controlled, consider either 1 dose reduction of sunitinib or stopping sunitinib
 
NOTE: Stopping or reducing the dose of sunitinib is expected to cause a decrease in BP the treating physician should monitor the patient for hypotension and adjust the number and dose of antihypertensive medication(s) accordingly.
		

Grade (CTCAE v4)	Antihypertensive Therapy	Blood Pressure Monitoring	Sunitinib Dose Modification

Persistent Grade 3 Severe Systolic ≥ 160 Diastolic ≥ 100
 
Protocol-specific guidance supersedes any other management guidelines, including CTCAE v4
	
HOLD sunitinib until systolic BP ≤ 159 and diastolic BP ≤ 99.
 
BP management is identical to that for Grade 2 (see steps 1-4 above) with 2 major exceptions:
 
1) If systolic BP >180 or diastolic BP >110 and the patient is symptomatic: optimal management with intensive IV support in ICU; STOP sunitinib and notify hospital staff that stopping sunitinib may result in a decrease in BP and
 
2) If systolic BP >180 or diastolic BP >110 and the patient is asymptomatic, 2 new anti-hypertensives must be given together in step 1 (and dose escalated appropriately as in step 1).
 
NOTE: Stopping or reducing the dose of sunitinib is expected to cause a decrease in BP the treating physician should monitor the patient for hypotension and adjust the number and dose of antihypertensive medication(s) accordingly
	
BP should be monitored as recommended by the treating physician unless the patient is symptomatic with systolic BP >180 or diastolic BP >110 in which case, monitoring should be intensive.
	
HOLD sunitinib until systolic BP ≤ 159 and diastolic BP ≤ 99.
 
In most circumstances, if BP cannot be controlled after an optimal trial of anti-hypertensive medications, consider either 1 dose reduction of sunitinib or stopping sunitinib. HOWEVER, if the patient requires hospitalization for management of symptomatic systolic BP >180 or diastolic BP >110, permanently discontinue sunitinib or if BP is controlled, re-start sunitinib at 1 lower dose level after consultation with the study Principal Investigator

Grade 4 Life-threatening consequences of hypertension
	
Optimal management with intensive IV support in ICU; STOP sunitinib and notify hospital staff that stopping sunitinib may result in a decrease in BP
	
Intensive
	
Permanently discontinue sunitinib or if BP is controlled, re-start sunitinib at 1 lower dose level after consultation with the study

Grade (CTCAE v4)	Antihypertensive Therapy	Blood Pressure Monitoring	Sunitinib Dose Modification
			Principal Investigator

Abbreviations: dihydropyridine calcium-channel blockers (DHP-CCB), selective beta blockers (BB), angiotensin converting enzyme inhibitors (ACEI), angiotensin II receptor blockers (ARB), alpha beta blocker (ABB)
 
 • *See table below for suggested antihypertensive medications by class • If patients require a delay of >2 weeks for management of hypertension, discontinue protocol therapy • If patients require >2 dose reductions, discontinue protocol therapy • Patients may have up to 2 drugs for management of hypertension prior to any dose reduction in sunitinib • 24-48 hours should elapse between modifications of anti-hypertensive therapy • Hypertension should be graded using CTCAE v4. 			

3.3.2 Everolimus

3.3.2.1 Hepatic impairment dose modifications

Please see **Appendix G** for determination of Child-Pugh classifications.

- Mild hepatic impairment (Child-Pugh A) – the recommended starting dose is 7.5 mg daily.
- Moderate hepatic impairment (Child-Pugh B) – the recommended starting dose is 5 mg daily.
- Severe hepatic impairment (Child-Pugh C) – not recommended. If the desired benefit outweighs the risk, a dose of 2.5 mg daily must not be exceeded.
- Dose adjustments should be made if a patient’s hepatic (Child-Pugh) status changes during treatment.

3.3.2.2 Dose delay

Everolimus treatment will be discontinued if a dose interruption exceeds 4 weeks (28 days).

3.3.2.3 Dosing modifications

For patients who do not tolerate the protocol-specified dosing schedule, dose adjustments are permitted in order to allow the patient to continue the study treatment. Details of study treatment schedule adjustments and dose levels are provided in **Table 7**

Table 7: Everolimus Dose Levels

Dose Level	Daily Dose	Dispensed As
0 – Starting dose level for patients without hepatic impairment*.	10 mg	1 x 10 mg tablets or 2 x 5 mg tablets or 4 x 2.5 mg tablets
-1	5 mg	1 x 5 mg tablets or

		2 x 2.5 mg tablets
-2	5 mg every other day‡	1 x 5 mg tablets or 2 x 2.5 mg tablets
*See Section 3.3.2.1 for definition and starting doses for hepatic impairment.		
‡ Patients requiring dose reduction below this level will be removed from the study therapy		

If treatment is interrupted due to toxicity, everolimus should not be resumed until recovery to grade ≤ 1 , then reintroduce everolimus at the initial dose or lower dose level depending on toxicity type and Grade.

If a patient has already decreased 2 dose levels, no further dose reduction is permitted. Patients requiring a third dose reduction will be required to discontinue study treatment. The following Table provides the procedure to be followed for dose modification and re-initiation of everolimus in the event of toxicities suspected to be related to the study drug.

Table 8 and **Table 9** list the dosing guidelines for everolimus-related non-hematologic and hematologic toxicities.

Management of severe or intolerable adverse drug reactions (ADRs) may require temporary dose interruption (with or without dose reduction) of everolimus therapy.

The following sections summarize recommendations for dose interruption, reduction, or discontinuation of everolimus in the management of ADRs. General management recommendations are also provided as applicable. Clinical judgment of the treating physician should guide the management plan of each patient based on individual benefit/risk assessment.

Table 8: Dosing guidelines for everolimus-related non-hematologic toxicities

Toxicity	Action
Non-Infectious Pneumonitis	Please refer to 4.1.2.9
Reactivation of HBV or HCV flare	Please refer to 4.1.2.10
AST or ALT elevation Grade 1 (> ULN - 3.0 x ULN) Grade 2 (> 3.0 - 5.0 x ULN)	Maintain current dose level
AST or ALT elevation Grade 3 (> 5.0 - 20.0 ULN)*	Interrupt everolimus administration until resolution to \leq grade 1 (or \leq grade 2 if baseline values were within the range of grade 2). If resolution occurs within ≤ 7 days, everolimus should be re-started at the dose level prior to interruption. If resolution takes > 7 days, or if event reoccurs within 28 days, hold everolimus until recovery to \leq grade 1 or baseline grade / value and reintroduce everolimus at one dose level lower. .
AST or ALT elevation Grade 4 (> 20 x ULN)*	Interrupt everolimus administration until resolution to \leq grade 1 (or \leq grade 2 if baseline values were within the range of grade 2). If resolution occurs within ≤ 7 days, everolimus should be re-started at one dose level lower. If resolution takes > 7 days, discontinue everolimus.

Toxicity	Action
Intolerable grade 2 mucositis, or grade 3 AE, except hyperglycemia or hypertriglyceridemia or hypercholesterolemia (see Section 4.1.2.6)	Interrupt everolimus administration until resolution to \leq grade 1 or baseline grade / value. If resolution occurs within \leq 7 days, everolimus should be re-started at the dose level prior to interruption. If resolution takes $>$ 7 days, or if event reoccurs within 28 days, hold everolimus until recovery to \leq grade 1 or baseline grade / value and reintroduce everolimus at one dose level lower.
Any other grade 4	Hold everolimus until recovery to grade \leq 1 or baseline value Reintroduce everolimus at one dose level lower, if available.
Grade 3 or 4 clinical liver failure (asterixis or encephalopathy/coma)	Discontinue everolimus
Recurrence of intolerable grade 2 mucositis or grade 3 event after dose reduction	Reduce dose to the next lower dose level, if available. The lowest possible dose level of everolimus is 2.5 mg daily. Below this level, everolimus must be discontinued. If toxicity recurs at Grade 3, consider discontinuation
Recurrence of grade 4 after dose reduction	Discontinue everolimus
Any non-hematologic toxicity requiring everolimus interruption for $>$ 28 days	Discontinue everolimus
* Should HCV flare be confirmed, the guidelines for flare must take precedence (4.1.2.10)	

Table 9 Dosing guidelines for Everolimus-related hematologic toxicities

Toxicity	Action
Grade 2 thrombocytopenia (platelets <75, ≥ 50x10 ⁹ /L)	No action
Grade 3 thrombocytopenia (platelets <50, ≥ 25 x10 ⁹ /L)	Interrupt everolimus until resolution to grade ≤1 If resolution occurs within ≤ 7 days, reintroduce everolimus at the dose level prior to interruption. If resolution occurs after more than 7 days, or event reoccurs within 28 days, reintroduce everolimus at one dose level lower.
Grade 4 thrombocytopenia (platelets < 25 x10 ⁹ /L)	Interrupt everolimus until recovery to grade ≤ 1. Then reintroduce everolimus at one dose level lower.
Grade 3 neutropenia or anemia (neutrophil <1, ≥0.5 x10 ⁹ /L)	Interrupt everolimus until resolution to grade ≤1 or baseline value If AE resolution occurs ≤ 7 days, reintroduce everolimus at the same dose level. If AE resolution occurs > 7 days, or event reoccurs within 28 days, reintroduce everolimus at one dose level lower.
Grade 4 neutropenia or anemia	Interrupt everolimus until recovery to grade ≤ 1 or baseline value. Reintroduce everolimus at one dose level lower.*
Febrile neutropenia	Interrupt everolimus until resolution to grade ≤ 1 (or baseline value) and no fever. Reintroduce everolimus at one dose level lower.*
Recurrence of grade 3 toxicity after dose reduction	Reduce dose to the next lower dose level, if available. The lowest possible dose level of everolimus is 5 mg every other day (2.5 mg daily). Below this level, everolimus must be discontinued
*Recurrence of grade 4 toxicity (including febrile neutropenia) after dose reduction	Discontinue everolimus
*Any hematologic toxicity requiring everolimus interruption for > 28 days	Discontinue everolimus

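### After a first everolimus-related grade 3–4 hypersensitivity reaction that clears within 28 days, the written default is to restart everolimus

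*Combined protocol and SAP*

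**What the plan says.** Section 3.3.2.3 introduces the everolimus toxicity tables as the "procedure to be followed for dose modification and re-initiation of everolimus" when a toxicity is suspected to be drug-related. Table 8 covers the non-hematologic events. Pneumonitis, hepatitis B or C reactivation, transaminase elevation and clinical liver failure have rows of their own. Hypersensitivity, anaphylaxis and angioedema do not.

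Two rows catch whatever is not named:

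- **Grade 3.** The row is labelled "Intolerable grade 2 mucositis, or grade 3 AE, except hyperglycemia or hypertriglyceridemia or hypercholesterolemia (see Section 4.1.2.6". If the event resolves within 7 days, "everolimus should be re-started at the dose level prior to interruption". If it takes longer, or recurs within 28 days, the drug returns one level lower.
- **Any other grade 4.** Hold until recovery, then "Reintroduce everolimus at one dose level lower, if available".

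Section 4.1.2.3 has a title promising management of hypersensitivity reactions. Its one sentence lists possible manifestations, anaphylaxis and airway swelling among them, and says they have been seen with everolimus. Section 4.1.2.4 notes a possibly higher angioedema risk with ACE inhibitors. Neither tells the physician to hold, stop or avoid rechallenge.

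**The concern.** A physician who follows Table 8 after a severe allergic reaction to everolimus is led back to the same drug, in one case at the full dose. The section where an exception would be expected contains none. The stake is the safety of the individual patient on re-exposure.

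The gap stands out for two reasons. Exclusion 2.1.2.7 keeps out people with a history of allergy to compounds similar to either drug, so the protocol treats allergy as serious at entry. In addition, the sunitinib hypertension steps in Table 6 allow an ACE inhibitor as an added drug, and Table 10 lists seven. A patient on one may later cross over to everolimus and so fall into the group that 4.1.2.4 warns about.

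**Working it through.** The plan gives no figure to reproduce, so this is a trace through the text.

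**Inputs.** Table 7: level 0 is 10 mg daily, level -1 is 5 mg daily, level -2 is 5 mg every other day, and below that study therapy ends. Section 3.3.2.2: "Everolimus treatment will be discontinued if a dose interruption exceeds 4 weeks (28 days". I use this everolimus-specific limit rather than the general 12-week allowance that opens section 3.3.

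**Step 1: which row applies.** The exceptions in the grade 3 row are metabolic only, so a related grade 3 reaction stays in it. A related grade 4 reaction is not a transaminase, liver-failure, pneumonitis or hepatitis event, so it falls under any other grade 4.

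**Step 2: first event, patient on 10 mg.**

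| Grade | Clears in | Level afterwards | Written action |
|---|---|---|---|
| 3 | 7 days or less | 0 | restart at 10 mg daily |
| 3 | 8–28 days | -1 | restart at 5 mg daily |
| 4 | 28 days or less | -1 | restart at 5 mg daily |
| 3 or 4 | more than 28 days | none | stop |

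Every branch that clears within 28 days ends in a restart. Time to clearance changes the dose for grade 3 only.

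**Step 3: lower starting levels.** From level -1 the same three restart branches give 5 mg daily, 5 mg every other day and 5 mg every other day. From level -2, a grade 3 event cleared within 7 days restarts at the same level. The other two branches need a further reduction, so treatment stops.

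**Step 4: do the general stops prevent re-exposure?**

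- The 28-day limit does not reach a reaction that clears sooner.
- "Recurrence of grade 4 after dose reduction" leads to discontinuation, but only after the drug has been given again.
- "Patients requiring a third dose reduction will be required to discontinue study treatment": this needs two earlier reductions, whether from re-exposure or from another toxicity.
- A grade 3 event recurring after a reduction goes to the next lower level, with the softer instruction "If toxicity recurs at Grade 3, consider discontinuation".

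For a patient at level 0 or -1, none of these acts on a first reaction that clears within 28 days.

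**Step 5: comparison within section 4.1.2.** Of the ten subsections, five contain a stop at the first event: 4.1.2.1 (invasive fungal infection), 4.1.2.6 (grade 4 stomatitis), 4.1.2.8 (grade 4 metabolic events), 4.1.2.9 (grade 4 pneumonitis) and 4.1.2.10 (hepatitis C flare). Three give supportive care or monitoring only (4.1.2.2, 4.1.2.5, 4.1.2.7). Two give no action (4.1.2.3, 4.1.2.4). 5 + 3 + 2 = 10. As written, grade 4 stomatitis stops everolimus, while a grade 4 allergic reaction leads to a reduced-dose restart.

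**Step 6: the cross-over route.** Sections 2.3.1 and 3.1.1 send patients with unacceptable treatment-related toxicity to the other drug. Section 3.5.1 refers to section 3.3 for what that means, but 3.3 defines nothing under that name, does not mention hypersensitivity, and contains Table 8 itself.

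**The case against.** The strongest reply is that the protocol already lets the physician stop. Table 8 is titled as guidelines. Section 3.3.2.3 describes what follows as recommendations and says clinical judgment should guide each patient's plan. Section 3.5.1 lists investigator discretion. Section 4.1 calls for standard medical therapy in managing toxicity, and section 7.4.1 has the team discuss each patient weekly during active treatment. All of this stands. A physician who stops after anaphylaxis is applying the plan, not departing from it. What does not follow is that the gap is closed: the same judgment clause covers stomatitis and pneumonitis, for which the protocol still wrote stop rules. Exclusion 2.1.2.7 applies at entry and does not govern restarting after an on-study reaction.

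The objection on frequency also stands. No incidence is given, and hypersensitivity is not among the common reactions in 4.1.2 or 11.2.4. Nor is it the only toxicity without a stop rule: renal failure (4.1.2.5) gets monitoring only.

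A reader might infer that rechallenge after anaphylaxis is compulsory; the judgment and discretion clauses rule that out. A reader might also infer that the faster any reaction clears, the higher the restart dose. That holds for grade 3 only, because the grade 4 row has no time element. Nor do the documents support extending the point to sunitinib. Table 5 does resume sunitinib at the same dose after a first grade 3 event, but the protocol reports hypersensitivity as an observed reaction only for everolimus.

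**Conclusion.** The concern holds as a statement about the written default. For a first everolimus-related grade 3–4 hypersensitivity reaction clearing within 28 days, the protocol points to restarting everolimus, and no hypersensitivity-specific rule overrides that. From the 10 mg start the dose is 10 mg daily in one branch and 5 mg daily in two. The exception is a patient at level -2 who needs a further reduction and must stop.

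This rests on three readings: the reaction is judged drug-related, unnamed events fall into the general rows, and the 28-day everolimus limit governs. Few patients are expected to be affected. The consequence is for their safety; nothing here bears on the PFS analysis. It is a cheap improvement worth making because the possible harm is severe.

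**What to change.** Make three small text changes in one amendment:

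1. **Table 8.** Add a row in the format used for pneumonitis: *Hypersensitivity, anaphylaxis or angioedema: please refer to 4.1.2.3.*
2. **Section 4.1.2.3.** Add: *Permanently discontinue everolimus, without rechallenge, after an everolimus-related grade 3–4 hypersensitivity reaction or anaphylaxis; treat as unacceptable toxicity under 3.1.1. For this cross-over, a reaction to everolimus alone does not exclude the patient from sunitinib under 2.1.2.7. If everolimus was the second drug, end protocol therapy.*
3. **Section 4.1.2.4.** Add a cross-reference to 4.1.2.3 and leave ACE-inhibitor handling to the investigator. The documents give no basis for a more detailed rule.

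The sentence on 2.1.2.7 is needed because 3.1.1 requires eligibility to be confirmed before cross-over, and that exclusion could be read as barring a patient who has just reacted to everolimus.

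The change adds no visits or procedures and does not alter the sample size. Its cost is that a few patients who might have tolerated rechallenge will leave everolimus.

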4.1.2.6 Management of stomatitis / oral mucositis / mouth ulcers

Adverse Drug Reaction	Severity	Everolimus Dose Adjustment and Management Recommendations
Stomatitis	Grade 1 (Minimal symptoms, normal diet)	No dose adjustment required. Manage with non-alcoholic or salt water (0.9%) mouth wash several times a day.
	Grade 2 (Symptomatic but can eat and swallow modified diet)	Temporary dose interruption until recovery to grade ≤ 1 . Re-initiate everolimus at the same dose. If stomatitis recurs at grade 2, interrupt dose until recovery to grade ≤ 1 . Re-initiate everolimus at one dose level lower. Manage with topical analgesic mouth treatments (e.g. benzocaine, butyl aminobenzoate, tetracaine hydrochloride, menthol or phenol) with or without topical corticosteroids (i.e. triamcinolone oral paste)*.
	Grade 3 (Symptomatic and unable to adequately eat or hydrate orally)	Temporary dose interruption until recovery to grade ≤ 1 . Re-initiate everolimus at one dose level lower. Manage with topical analgesic mouth treatments (i.e. benzocaine, butyl aminobenzoate, tetracaine hydrochloride, menthol or phenol) with or without topical corticosteroids (i.e. triamcinolone oral paste)*
	Grade 4 (Symptoms associated with life-threatening consequences)	Discontinue everolimus and treat with appropriate medical therapy.

* using agents containing alcohol, hydrogen peroxide, iodine, and thyme derivatives in management of stomatitis as they may worsen mouth ulcers.

Patients with a clinical history of stomatitis/mucositis/mouth ulcers and those with gastrointestinal morbidity associated with mouth/dental infections, irritation of esophageal mucosa e.g. gastroesophageal reflux disease (GERD) and pre-existing stomatitis/mucositis must be monitored even more closely. Patients should be instructed to report the first onset of buccal mucosa irritation/reddening to their study physician immediately.

Stomatitis/oral mucositis/mouth ulcers due to everolimus should be treated using local supportive care. Please note that investigators in earlier trials have described the oral toxicities associated with everolimus as mouth ulcers, rather than mucositis or stomatitis. If your examination reveals mouth ulcers rather than a more general inflammation of the mouth, please classify the adverse event as such. The suggested paradigm for treatment of stomatitis/oral mucositis/mouth ulcers is as follows:

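### After a first grade 4 stomatitis or metabolic event that recovers within 28 days with a lower dose level left, Table 8 restarts everolimus while 4.1.2.6 and 4.1.2.8 stop it, and no clause says which governs

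*Combined protocol and SAP*

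**What the plan says.** **Table 8 (section 3.3.2.3).** The table covers everolimus-related non-hematologic toxicities. It has its own entries for pneumonitis, hepatitis B or C reactivation or flare, AST/ALT elevation and clinical liver failure. Any remaining grade 4 event is held until grade 1 or baseline, and then: "Reintroduce everolimus at one dose level lower, if available". A separate row, "Recurrence of grade 4 after dose reduction", leads to discontinuation, as does any interruption beyond 28 days.

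**Section 4.1.2.6 (stomatitis, oral mucositis, mouth ulcers).** Grade 4 is defined as "Symptoms associated with life-threatening consequences", and the action is "Discontinue everolimus and treat with appropriate medical therapy".

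**Section 4.1.2.8 (hyperlipidemia and hyperglycemia).** The action for a grade 4 metabolic event is also discontinuation.

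**Links between the two places.**
- Table 8 sends pneumonitis to the management section ("Please refer to 4.1.2.9") and does the same for hepatitis B and C.
- Its only precedence note concerns hepatitis C: "Should HCV flare be confirmed, the guidelines for flare must take precedence (4.1.2.10").
- Its only mention of lipid and glucose events is an exception in the grade 3 row: "Intolerable grade 2 mucositis, or grade 3 AE, except hyperglycemia or hypertriglyceridemia or hypercholesterolemia (see Section 4.1.2.6").

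**The concern.** A clinician facing a first grade 4 stomatitis or metabolic event finds two instructions that cannot both be followed. One restarts the drug at a reduced dose once the event settles; the other ends it. A clinician who follows Table 8 to the letter re-exposes the patient after a toxicity for which the protocol's own management section stops everolimus. For stomatitis, that toxicity is defined as life-threatening.

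The choice also determines the patient's path through the trial. Under section 3.1.1, unacceptable treatment-related toxicity leads to cross-over. An Arm 2 patient with such an event would therefore stay on first-line everolimus under one instruction and move to sunitinib under the other. Two clinicians could handle identical patients differently, each with support in the text.

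**Working it through.** The plan states no figure on this point to reproduce. The check compares the instructions and then bounds the number of patients.

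**Step 1. Which Table 8 row applies?** Mucositis is named in Table 8 only at intolerable grade 2, in a row shared with grade 3 events, and in the row for recurrence of those events. Hyperglycemia, hypertriglyceridemia and hypercholesterolemia are named only as exceptions in that shared row. Neither group has a grade 4 entry, so both fall into the catch-all grade 4 row.

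**Step 2. Side by side, first event.**

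| Event | Table 8 | Management section |
|---|---|---|
| Grade 4 stomatitis | Hold, then restart one level down | 4.1.2.6: stop |
| Grade 4 hyperglycemia or dyslipidemia | Hold, then restart one level down | 4.1.2.8: stop |

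**Step 3. When do the two diverge?** Table 8 also stops everolimus, or gives no restart, when:
- the interruption exceeds 28 days (Table 8 and section 3.3.2.2);
- no lower dose level remains (the restart is conditional on one, and section 3.3.2.3 requires discontinuation if a third reduction would be needed);
- grade 4 recurs after a dose reduction.

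The conflict is what remains: a first grade 4 event that recovers to grade 1 or baseline within 28 days, with a lower level available.

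**Step 4. Does anything resolve it?**
- The referrals to 4.1.2 cover pneumonitis and hepatitis B and C only.
- The precedence note covers hepatitis C flare only.
- The lipid and glucose exception does not reach grade 4. Its pointer is to 4.1.2.6, which has no lipid or glucose rule; that rule is in 4.1.2.8. If the pointer was meant for mucositis, it still sits in the grade 2 and 3 row.
- Section 3.3.2.3 says of what follows it: "The following sections summarize recommendations for dose interruption, reduction, or discontinuation of everolimus in the management of ADRs". Section 4.1 describes its own subsections as recommendations too. Neither is ranked above the other.

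**Step 5. How many patients?** Section 11.2.4 lists stomatitis and hyperglycemia among grade 3 and 4 reactions with an incidence of 1% to under 10% each. For the 44 patients planned per arm in section 8:
- lower end: 0.01 × 44 = 0.44
- upper end: below 0.10 × 44 = 4.4

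These are grades 3 and 4 together, for each event type. Grade 4 alone is not given and can be no higher. Taking 0.1%, 0.5% and 1% as assumed rates for one type of grade 4 event in 44 patients:

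| Assumed rate p | Expected, 44p | Chance of at least one, 1 − (1 − p)^44 |
|---|---|---|
| 0.1% | 0.04 | 4% |
| 0.5% | 0.22 | 20% |
| 1% | 0.44 | 36% |

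At any assumed rate these figures overstate the conflict in those 44 patients, because they count every grade 4 event and not only those meeting the Step 3 conditions. Patients who reach everolimus by cross-over would add to the number exposed; the documents do not say how many there will be.

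**The case against.** The strongest reply is that no clinician is forced to re-expose anyone. Section 3.3.2.3 makes clinical judgment the guide to each patient's management. Section 3.5.1 lists investigator discretion as a ground for removal from protocol therapy. Section 7.4.1 has the team discuss each patient weekly. The section on the named toxicity is also the more specific one and would naturally be followed. All of this lowers the risk. None of it says which instruction applies, and two places lean towards the less protective one: section 3.3.2.3 presents its table as the procedure for changing and restarting the dose, and section 3.5.1 refers to section 3.3 for what counts as unacceptable toxicity.

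A second reply is that the word other in the catch-all row excludes toxicities named in the row above it. That is possible, but the named row is confined to grades 2 and 3, so the reading is not compelled.

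Two stronger readings are tempting and should not be drawn.
- **Table 8 always allows one grade 4 event before stopping.** A reader might infer this from the recurrence row. It does not hold, because a first event can also end everolimus through the 28-day limit or the lack of a lower level.
- **The stomatitis rules conflict equally at grades 2 and 3.** They do differ. Grade 3 resolving within 7 days restarts at the prior dose in Table 8 but one level down in 4.1.2.6. Intolerable grade 2 lasting more than 7 days restarts one level down in Table 8, while 4.1.2.6 keeps the same dose after a first grade 2 episode. However, that Table 8 row carries a pointer to 4.1.2.6, which can be read as deferring to it, and Table 8 addresses only the intolerable subset of grade 2. These differences need tidying but are weaker than the grade 4 conflict.

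**Conclusion.** The conflict is real and narrow. For a first grade 4 stomatitis or metabolic event that recovers to grade 1 or baseline within 28 days with a lower dose level available, Table 8 restarts everolimus and sections 4.1.2.6 and 4.1.2.8 stop it, with no rule to choose between them. This rests on the text alone and needs no assumed rate.

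The number of patients is probably small. The documents bound it only through the combined grade 3 and 4 incidence; the lower rates in the working are assumptions.

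A reader might infer that the primary analysis is compromised because the instruction chosen affects how long a patient stays on first-line everolimus. The documents do not support that: the PFS definition in section 6.3.6 and the sample size in section 8 do not depend on this dosing rule. The point is one of patient safety and uniform conduct. It should be corrected by amendment.

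**What to change.** In Table 8:
- except grade 4 stomatitis or mucositis and grade 4 metabolic events from the catch-all grade 4 row, and refer them to 4.1.2.6 and 4.1.2.8 (discontinue), in the form already used for pneumonitis and hepatitis;
- point the lipid and glucose exception to 4.1.2.8;
- state that 4.1.2.6 governs the restart dose for stomatitis, so that grade 3 restarts one level down however quickly it resolves. If the sponsor wants Table 8's stricter handling of prolonged intolerable grade 2 mucositis, it should be written into 4.1.2.6.

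The cost is a few lines of amendment text, with no effect on data collection, sample size or analysis. The clinical downside is slightly more everolimus discontinuations or reductions. A first-line Arm 2 patient who stops can still cross over to sunitinib under section 3.1.1, once the toxicity has resolved to grade 1 or baseline and within its 3-month window. A patient who reached everolimus by cross-over would lose the last protocol drug, so the sponsor should make this choice knowingly.
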